tervention effect on children's determinants, mean scores on the various determinants will be calculated. Then, change scores (i.e., the difference in mean score between the baseline measurement and the follow-up measurements) will be calculated. Linear mixed model analyses will be used to assess the longitudinal effect of the intervention on the various determinants assessed in the questionnaire, as this method corrects for correlation within individuals within groups, which occurs in repeated-measures research designs. Another advantage of this technique is that it naturally handles missing values, in case data are missing at random. Since measurements are repeated within participants, who are nested within classes, we use a three-level model with classes as third level, participants as second level and measurements as first level. The fixed part of the model consists of group (intervention versus control), time (time-points at which the measurements are taken) and the interaction term group*time. Baseline variables that are related to missing data and/or outcome will also be included to obtain unbiased results and/or to gain precision. As for the random part of the model, a random intercept on class level will be included next to an unstructured covariance structure for the repeated measurements. Relative effect sizes will be calculated for each determinant. These will be expressed as Cohen's d: a Cohen's d of 0.2 is interpreted as a small, 0.5 as a medium and 0.8 as a large effect size (11).

1.3 How will humans be participants in the study (either directly or indirectly, for example, through the use of their personal data)?

All children from the intervention and control classes whose parents have given their consent are asked to fill in the questionnaires. Only anonymised data will be collected and used in the present study.

1.4 Does your study re-use data that has already been gathered for another project or purpose? If so, do you have permission to re-use that data, and was there the relevant consent for this re-use in the first study? (Please explain, with reference to, for example, previous ethics committee decisions and informed consent protocols.)

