In intervention classes, the data used in this study is collected as part of the Kokkerelli Learning Street. As only anonymised data will be used in the present study, the GDPR does not require the draft of a data transfer agreement or any other comparable agreement between Maastricht University and Kids University for Cooking BV.

In control classes, data is collected as part of another, larger study that will take place at the same time (further specified in an earlier section of this application). Ethical approval for this larger, ongoing study is under assessment by the Zuyderland Medical Ethics Committee. For both the intervention and control group, only data of participants whose parents/caregivers have given informed consent will be used in the present study. All anonymised data will be property of Maastricht University. The non-anonymised data (envelopes with ID number and child's name) are property of the school and will therefore remain at school after data collection to be destroyed.

1.5 What sort of people will be involved? (For example, professionals in the course of their profession, members of the general public.)

Participants will be children aged 8-10 years old (study years five) from primary schools in Limburg, the Netherlands. Parents of these children will be informed by Kids University for Cooking BV (intervention group) or researchers from Maastricht University (control group) about the study. They will receive an information brochure about the study and are asked to give written consent for their child's participation in the study.

1.6 On what grounds did you determine the number of participants needed for the study?

As one of the primary aims of the Kokkerelli Learning Street is to improve children's knowledge with regard to fruit and vegetables, it is expected that the Kokkerelli Learning Street will have positive effects on participants' knowledge. Therefore, the sample size calculation was based on the primary outcome, i.e. to detect a difference in knowledge score between the intervention classes and the control classes three months after the intervention. Unfortunately, limited evidence is available regarding the effects of the Kokkerelli Learning Street or comparable programmes on

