participants' knowledge. In 2014, Kasten et al. performed a one-group effect evaluation of the Kokkerelli Learning Street (10). In this study, the outcome measure that changed most significantly was the determinant knowledge (mean difference T2-T0: 0.41, SD: 0.93). However, this study did not include a control group and the outcomes therefore only indicate within-group differences instead of between-group differences, while the present study does include a control group. The following assumptions were used for the sample size calculation:

- Children are nested within school classes, with 25 participants per class, and seven intervention classes and seven control classes;
- A significance level (alpha) of 0.05;
- A power of 80%;
- Independent samples t-test on difference in knowledge scores;
- An Intraclass Correlation Coefficient of 0.04, based on values used by Battjes et al. (8);
- A dropout rate of 10%, as based on dropout rates observed by Bartelink et al. (12);
- An SD of 0.24 for the mean change in absolute knowledge score (T2-T0) in the population, as based on the effect evaluation of a comparable programme by Battjes et al. (8).

With these assumptions, we can demonstrate an effect size of 0.104 on absolute knowledge scores. The standardised effect size is then equal to $0.104/0.22 = 0.47$, indicating a small to medium effect size (11).

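### The planned class random intercept cancels from group*time, so a test of T2-T0 change in knowledge has no clustering correction; type I error is about 15% if the plan's ICC of 0.04 applies to change in both arms

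*Combined protocol and SAP*

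**What the plan says.** Section 1.2 (Data Processing and Statistical Analyses) describes a three-level linear mixed model: measurements within children within classes. The fixed part is group, "time (time-points at which the measurements are taken) and the interaction term group*time". For the random part, "a random intercept on class level will be included next to an unstructured covariance structure for the repeated measurements". The reply of 21-11-2019 gives the same model. Neither text mentions a class-by-time term, a cluster-robust standard error or a small-sample degrees-of-freedom method. Just before the model, section 1.2 says: "Then, change scores (i.e., the difference in mean score between the baseline measurement and the follow-up measurements) will be calculated". It does not say that these change scores are the outcome of the mixed model.

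Section 1.6 makes knowledge the primary outcome and sizes the study "to detect a difference in knowledge score between the intervention classes and the control classes three months after the intervention". Its assumptions include seven classes of 25 children per arm, 10% dropout, "Independent samples t-test on difference in knowledge scores", "An Intraclass Correlation Coefficient of 0.04" and "An SD of 0.24 for the mean change in absolute knowledge score (T2-T0) in the population". The result is a detectable difference of 0.104.

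**The concern.** The class intercept is the only term that represents clustering by class. It describes classes that score higher or lower than others by the same amount at every time point. It cannot describe classes that improve by different amounts, and that is the variation that matters when the effect is a group difference in change. Such variation is plausible here: each class's own teacher delivers the introduction and evaluation lessons, and the programme covers one of nine products.

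If classes do differ in how much they change, the standard error, confidence interval and p-value for group*time are too optimistic, and ordinary class-to-class variation could be reported as a programme effect. Section 1.7 says the evaluation is meant to support entry in a national database of effective interventions, so a false positive on knowledge would have consequences. The direction is the same for T1 and for the other determinants, but the documents give no ICC with which to size the problem there.

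**Working it through.** **Inputs (section 1.6).** 7 classes per arm; 25 × 0.9 = 22.5 children per class after dropout; 7 × 22.5 = 157.5 children per arm; ICC 0.04; SD of T2-T0 change 0.24; power 80%; alpha 0.05 (two-sided in section 1.2).

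**Step 1: reproduce 0.104.**
- Design effect = 1 + (22.5 − 1) × 0.04 = 1.86.
- SE = 0.24 × √(2 × 1.86 / 157.5) = 0.0369.
- Detectable difference = (1.960 + 0.842) × 0.0369 = 0.1033 by the normal approximation, or 0.1037 with t on 313 df. This matches the plan's 0.104.
- Without the design effect, SD 0.24 gives 0.076 (normal) to 0.083 (12 df).
- Section 1.6 standardises with a different SD (0.104/0.22 = 0.47; with 0.24 it would be 0.43). SD 0.22 on 12 df with the design effect gives 0.103. Without the design effect, SD 0.22 gives 0.069 to 0.076.

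On either SD, 0.104 requires the design effect applied to change.

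**Step 2: the cancellation.** Let the class intercept have variance τ². Its contribution to the class means at (T0, T1, T2) is τ²J, where J is the 3 × 3 matrix of ones. The T2-T0 contrast is c = (−1, 0, 1), so its contribution to the variance is c′(τ²J)c = τ²(−1 + 0 + 1)² = 0.

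Numerical check, generalised least squares with τ² = 0, 0.04, 0.1 and 0.3 (25 per class, unit variance, child correlation 0.3): the SE of the T2-T0 group*time contrast is √(2 × 1.4 / 175) = 0.1265 in all four cases. With 10% dropout it moves only from 0.13105 to 0.13109.

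**Step 3: type I error of that contrast.** The model's variance omits the design effect (DE), so actual alpha = 2 × [1 − Φ(1.96/√DE)], with DE = 1 + 21.5 × ICC of change.

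| ICC of change | DE | SE too small by | Type I error |
|---|---|---|---|
| 0 (constant class effects) | 1.00 | 1.00 | 5.0% |
| 0.01 | 1.215 | 1.10 | 7.5% |
| 0.02 | 1.43 | 1.20 | 10.1% |
| 0.04 | 1.86 | 1.36 | 15.1% |
| 0.08 | 2.72 | 1.65 | 23.5% |

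If change is clustered in one arm only at 0.04, the mean design effect is (1.86 + 1)/2 = 1.43, giving 10.1%. With 10% of T2 values missing and T0 and T1 kept, the ICC 0.04 figure is about 15.5%.

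**Step 4: simulation.** Two million draws with an estimated residual variance gave 15.1% at ICC 0.04. REML fits of the planned model gave 15.2% (4,800 trials) and 14.5% (1,500 trials). One set of 2,000 trials gave 12.8%; the valid 12-df test was also low in that set, at 4.0%. With constant class effects, REML fits gave 5.7% (2,500 trials).

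**Step 5: if the T2 level were tested instead.** The class intercept is then effective. REML fits on 12 df gave 3.4% (constant class effects), 6.1% (independent class-by-time effects) and 7.5% (class differences that arise at T1 and persist).

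**The case against.** The algebra is not in dispute; what the plan commits to is. The primary outcome in section 1.6 can be read as a difference in T2 level, and section 1.2 computes change scores just before describing the model. Under either reading the class intercept would not cancel, and the error would largely disappear. Nor do the documents say that 0.04 is an ICC of change: it comes from a cited source, and pairing it with an SD of change shows how it was used, not what it measures.

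If 0.04 is an ICC of levels, the inflation depends on how stable class differences are. With child correlation assumed at 0.3 to 0.7, type I error is 6.5–8.5% at a class autocorrelation of 0.9, 8–12% at 0.8 and 12–21% at 0.5.

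A further objection is practical. With 14 classes a richer class-level model often cannot be estimated, and a pure change-score analysis gives up part of the missing-data advantage for which the mixed model was chosen.

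What stands is that the 15% is conditional and that the primary contrast is inferred. The objection does not remove the concern. The written model has time as the measurement occasions and includes group*time, the sizing uses the SD of T2-T0 change, and the level-ICC figures all lie between 5% and 23%. If another contrast was intended, the plan needs to name it.

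**Conclusion.** The concern holds and must be fixed before analysis. Two parts are firm: the class intercept cancels from the T2-T0 group*time contrast, and section 1.6 applies a design effect of 1.86 to that same change. The sample size and the analysis therefore disagree about clustering.

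The size is less certain. Type I error for knowledge at T2 is about 15% if ICC 0.04 applies to change in both arms, 10% if in one arm only, 5% if class effects are constant over time, and about 23% at ICC 0.08. All of this assumes that group*time at T2 versus T0 is the test. If the T2 level is tested instead, the range is about 3% to 8%.

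**What to change.** 1. **Name the primary contrast:** the between-group difference in T2-T0 change in knowledge.
2. **Model class variation in that change directly.** Use T2-T0 change as the outcome, with a class random intercept, the planned baseline covariates and Satterthwaite degrees of freedom (about 12). If the model does not converge or the class variance is estimated at zero (9.6% of simulated trials at ICC 0.04, 36% at 0.01), use a t-test on class-mean changes with 12 df. With balanced data this procedure held 5.0% for ICC 0 to 0.08, and 5.2% with clustering in one arm. Do the same for T1-T0 and the other determinants.
3. **If the three-time-point model is kept,** add a class-level time effect with an unstructured class covariance and Satterthwaite df, and state that step 2 applies when it cannot be estimated. That will be common: the class covariance was not positive definite in 62–91% of simulated trials at ICC 0.04. A single pooled class-by-time variance is not enough; it gave 7.0–8.0% at ICC 0.04 when class differences persist or grow.
4. **In section 1.6,** reconcile SD 0.24 with 0.22, say which df gave 0.104, and restate power for the df used.

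**Cost.** Only plan wording and model syntax change. Confidence intervals widen. At ICC 0.04 and 12 df, power for 0.104 is about 73.5% with SD 0.24 (detectable difference 0.113), or 80.6% with SD 0.22 (0.103). Leaving out children without T0 or T2 makes the SE about 1–2% larger with 10% missing T2 (child correlation 0.3 to 0.7, assumed), and the missing-at-random assumption then rests on the baseline covariates without T1. The class-mean fallback also loses child-level covariate adjustment.

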After the T2 measurement, the envelopes with filled-in questionnaires are collected by Kids University for Cooking BV (intervention group) or researchers (control group). The envelopes with the ID number and name of the child, in which the blank questionnaires were stored, are not collected and will remain at the school. This means that only anonymised data will be collected, all non-anonymised data (envelopes with ID number and child's name) will remain at school. Researchers therefore only have access to the anonymised data. All anonymised data will be delivered to the principal researcher at Maastricht University.

In the data analyses, the mean scores of the answers on the questions will be used. Since single unrelated questions will be asked to test different aspects of knowledge, a score of correct answers will be used in further analyses of this determinant.

Data will quantitatively be analysed using IBM SPSS Statistics for Windows (version 25, IBM Corp, Armonk, NY, USA). Numerical variables will be presented as mean \pm standard deviation (SD), where number (%) will be used for categorical variables. A two-tailed test is considered statistically significant with p-values ≤ 0.05 . Questionnaire items for the determinants knowledge, intention, attitude, skills and taste preferences are combined into one variable per determinant for each time point. Differences in numerical baseline parameters between the control and intervention group will be tested with the independent-samples t-test or Mann-Whitney U-test where appropriate, while the Chi-square test, or Fisher's exact test, will be used for categorical variables. To investigate the in-

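### Section 1.6 assumes an SD of 0.24 but standardises by 0.22 and gives no degrees of freedom; with 0.24, the printed 0.104 and 0.47 cannot both hold

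*Combined protocol and SAP*

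**What the plan says.** Section 1.6 sets out the assumptions for the primary outcome, the knowledge score three months after the intervention. The layout is children nested in classes, "with 25 participants per class, and seven intervention classes and seven control classes". The test is given as "Independent samples t-test on difference in knowledge scores", with no degrees of freedom and no statement of whether the child or the class is the unit. The other inputs are an alpha of 0.05, 80% power, an intraclass correlation of 0.04, 10% dropout, and "An SD of 0.24 for the mean change in absolute knowledge score (T2-T0) in the population".

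The result follows: "With these assumptions, we can demonstrate an effect size of 0.104 on absolute knowledge scores". The next sentence reads: "The standardised effect size is then equal to $0.104/0.22 = 0.47$, indicating a small to medium effect size".

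Section 1.6 does not say whether alpha is one- or two-sided. The statistical analysis text in section 1.2 does: "A two-tailed test is considered statistically significant with p-values" at or below 0.05. That text also gives the benchmarks behind the verbal label: "d of 0.2 is interpreted as a small, 0.5 as a medium and 0.8 as a large effect size".

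**The concern.** The detectable difference is said to follow from the listed assumptions, which include an SD of 0.24, yet it is standardised by 0.22. The document neither derives nor explains 0.22. A misprinted divisor alone would not explain this, because the printed quotient of 0.47 is what division by 0.22 gives.

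The missing degrees of freedom make the slip hard to resolve. Whole classes either take part in the Learning Street or do not, and there are seven on each side, so a class-level test has 2 x 7 - 2 = 12 degrees of freedom. A design effect inflates the variance for clustering but does not account for estimating that variance from only 14 classes. Depending on which SD is right and whether 12 degrees of freedom were used, the claim of 80% power at 0.104 is correct, too high or too low. Section 1.6 is the only quantitative support offered for the size of the study.

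**Working it through.** **Inputs (section 1.6 unless noted).** Seven classes per group; 25 children per class; ICC 0.04; dropout 10%; alpha 0.05, two-sided (section 1.2); power 80%; SD 0.24 as listed or 0.22 as used in the division. How dropout was applied is not stated, so I take 25 x 0.9 = 22.5 children per class and also 22 (rounded down).

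**The printed division.**
- 0.104/0.22 = 0.473, so the division itself is correct.
- 0.104/0.24 = 0.433.
- Rounding does not close the gap. With 0.104 between 0.1035 and 0.1045 and 0.47 between 0.465 and 0.475, the SD must lie between 0.1035/0.475 = 0.218 and 0.1045/0.465 = 0.225. That excludes 0.24. The ratio of the two printed figures does not depend on the test, so no choice of degrees of freedom rescues the pair with SD 0.24.

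**Effective sample size.** Design effect DE = 1 + (m - 1) x 0.04.
- m = 22.5: DE = 1 + 21.5 x 0.04 = 1.86; n per group = 7 x 22.5 = 157.5; effective n = 157.5/1.86 = 84.7.
- m = 22: DE = 1 + 21 x 0.04 = 1.84; n per group = 154; effective n = 154/1.84 = 83.7.

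**Detectable difference** = multiplier x SD x sqrt(2/effective n). The multiplier for 80% power is 2.802 with the normal approximation and 3.053 with the noncentral t on 12 df. The square root is 0.1537 (m = 22.5) or 0.1546 (m = 22). For example, 2.802 x 0.24 x 0.1537 = 0.1033, and 3.053 x 0.24 x 0.1537 = 0.1126.

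| Test | SD 0.24 (m = 22.5 / 22) | SD 0.22 (m = 22.5 / 22) | Standardised (m = 22.5 / 22) |
|---|---|---|---|
| Normal | 0.1033 / 0.1039 | 0.0947 / 0.0953 | 0.431 / 0.433 |
| t, individual df (313 / 306) | 0.1037 / 0.1043 | 0.0950 / 0.0956 | 0.432 / 0.434 |
| t, effective df (167 / 165) | 0.1039 / 0.1045 | 0.0953 / 0.0958 | 0.433 / 0.436 |
| t, 12 df | 0.1126 / 0.1133 | 0.1032 / 0.1038 | 0.469 / 0.472 |

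**Power at a true difference of 0.104 (m = 22.5 / 22).**
- SD 0.24, normal: 80.5% / 80.1%.
- SD 0.24, 12 df: 73.5% / 73.0%.
- SD 0.22, 12 df: 80.6% / 80.1%.
- SD 0.22, large-sample: 86.0% to 86.8% over the three large-sample variants.

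**Reading the table.** With SD 0.24, 0.104 appears only in the large-sample rows and 0.47 only in the 12-df row. With SD 0.22, both appear on 12 df: 0.104 and 0.47 at 22 children per class, and 0.103 and 0.47 at 22.5.

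**The label.** Both 0.43 and 0.47 lie between 0.2 and 0.5, so the small-to-medium description stands.

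**The case against.** The strongest objection is that 0.22 might be a different SD, for instance that of the knowledge score itself rather than of its change. Then 0.104 (SD 0.24, large-sample) and 0.47 (divisor 0.22) could both be right, and the fault would be an undefined divisor. The text does not support this: it mentions only one SD for the calculation and presents 0.47 as following from it. Even if true, 0.22 would have to be named and sourced, and the degrees of freedom would still be missing.

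Three narrower points have some force.
- The two readings do not fit equally well. At 22.5 children per class, SD 0.22 on 12 df gives 0.1032, which prints as 0.103; 0.104 needs rounding down to 22. SD 0.24 with a large-sample t-test gives 0.104 directly. This leans slightly towards 0.24 as the SD behind 0.104, but it depends on an unstated treatment of dropout and leaves 0.47 unexplained.
- The 73% describes a class-level t-test, not the planned mixed model. A class intercept that is constant over time drops out of the T2-T0 contrast, so that model would not generally test it on 12 df. That is true, but section 1.6 bases its calculation on a t-test with nesting and an ICC, and the figure should be read in that setting.
- Seven classes per group is an input, and section 1.2 defines the intervention group as all study-year-five classes taking part for the first time in 2019-2020. Availability may therefore have set the number. The detectable difference and power claimed for that number still need to be right.

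**Conclusion.** The concern holds. Section 1.6 contradicts its own SD, and with the listed 0.24 the pair 0.104 and 0.47 cannot be obtained on any degrees of freedom. If 0.24 is right, either 0.47 should be about 0.43 or 0.104 should be about 0.113. On 12 degrees of freedom, power at 0.104 is then 73.0% to 73.5%, not 80%. If 0.22 is right and 12 degrees of freedom were used, the printed results stand and only the assumption list is wrong. The documents do not settle which applies.

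These figures assume a two-sided alpha of 0.05, equal class sizes, and 10% dropout leaving 22 to 22.5 children per class. The effect-size label and the design are unaffected. The reported power and its reproducibility are affected.

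**What to change.** Check the SD against the cited effect evaluation and use that one value throughout section 1.6. State that alpha is two-sided, how dropout was applied, and that the calculation uses 12 degrees of freedom (2 x 7 - 2). Then print the matching figures:

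- **If the SD is 0.24:** a detectable difference of about 0.113 (standardised 0.47) at 80% power, or 0.104 (standardised 0.43) at about 73% power.
- **If the SD is 0.22:** change the assumption list to 0.22 and keep 0.104, 0.47 and 80%.

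If 0.22 proves to be the SD of some other quantity, name it and give its source. The cost is a rewording of section 1.6, with no extra classes or children. Under 0.24 the stated figures become slightly less favourable; under 0.22 only the list changes and the degrees of freedom are added.
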